Confusion Assessment Method for the Intensive Care Unit (CAM-ICU, Appendix C)	Patient	1 min	X	X		
Delirium Assessment Battery (Appendix G)	Patient	5 min	X	X		
Richmond Agitation Sedation Scale (RASS, Appendix H)	Patient	Observation	X	X		
Delirium Motor Subtyping Scale-4 (DMSS-4, Appendix I)	Patient	Observation	X	X		
Confusion Assessment Method Severity (CAM-S, Appendix J)	Patient	Observation	X	X		
Blood and urine [#]	Patient	5 min	X	X		
Demographics, education, substance abuse, sensory impairment, recent hospitalization, region of residence, highest occupation, height, weight, hospitalization in past 6-months.	Patient / Informant	5 min	X			
Quick Dementia Rating Scale (QDRS, Appendix K)	Informant	3 min	X			
Everyday Cognition (eCOG, Appendix U)	Informant	5 min	X			
Montreal Cognitive Assessment (Appendix V)	Patient	5 min	X	X ^o		X
Older American Resources and Services Activities of Daily Living Scale (OARS ADL, Appendix L)	Patient / Informant	5 min	X			X
Mini-Nutritional Assessment (Appendix M)	Patient / Informant	2 min	X			
Clinical Frailty Scale (Appendix N)	Patient	Observation	X			X
Hopkins Rehabilitation Engagement Rating Scale (Appendix E)	Patient	Observation		X*	X*	
Life Space Assessment (Appendix F)	Patient/ Informant	5 min	X			X
Repeatable Battery for the Assessment of Neuropsychological Status (RBANS, Appendix O)	Patient	30 min				X

DKEFS Proverbs (Appendix P)	Patient	4 min				X
DKEFS Color-Word Interference (Appendix Q)	Patient	3 min				X
DKEFS Category Switching (Appendix R)	Patient	3 min				X
Trails A and B (Appendix W)	Patient	5 min				X
EQ-5D-5L (Appendix S)	Patient / Informant	5 min				X
Death, nursing home placement, or rehospitalization	Patient / Informant / Medical record	2 min				X
Brain MRI	Patient	45 min				X
Propositional density	Patient writing sample [^]	None	X			

Table 4. Prospective data collection schedule. ^o MOCA to be performed at 120 hours or at hospital discharge, whichever comes first. ^{\$} hospital discharge only. ^{*}To be performed at hospital discharge and after the cognitive rehabilitation sessions are completed. #, Blood and urine will be collected at enrollment and 72 hours; 120 hour blood and urine is optional. [^]Home writing samples will be used to calculate propositional density.

“Observation” in the “Duration” column indicates that these measures are obtained by observing the patient during routine research activities.

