To account for **pre-illness cognition**, we will obtain the **Quick Dementia Rating Scale (QDRS, Appendix K)** and **Everyday Cognition (eCOG, Appendix U)** scales from a qualified informant (caregiver, offspring, spouse, sibling, or having known the patient >5 years). A qualified informant is present in 97% of delirious ED patients. **Pre-existing ADRD** will be defined as a

QDRS > 5.0, ADRD documented in the medical record, or prescribed an acetylcholine esterase inhibitor (galantamine, donepezil, and rivastigmine) before randomization.

We will also account for ***pre-morbid intelligence***, which is considered a measure of cognitive reserve, by calculating ***propositional density*** using the patient's writing samples written prior to the acute illness. Propositional density is the number of propositions per 10 words, and its measurement early and late in life has been shown to be strongly associated with future dementia status.^{53,54} We will use the Computerized Propositional Idea Density Rater (CPIDR version 3.2, Athens, GA) to calculate propositional density automatically.^{55,56} While propositional density remains stable over time even in patients with dementia,⁵⁷ We will attempt to collect the earliest writing samples available. Based on our pilot study, approximately 90% of older ED patients with a qualified informant will have writing samples available for analysis.

5.2.d. Additional prospective data collected at enrollment.

To ascertain ***pre-illness function***, we will collect the ***Older American Resources and Services Activities of Daily Living (OARS ADL, 2 min, Appendix L)*** at enrollment from the patient or qualified informant.⁵⁸ Scores range from 0 (completely dependent) to 28 (completely independent). ***Nutritional status*** will be determined by the ***Mini-Nutritional Assessment (MNA, Appendix M)***.⁵⁹ The MNA ranges from 0 (malnourished) to 14 (normal nutritional status). We will also determine ***pre-illness frailty*** using the ***Clinical Frailty Scale (Observational, Appendix N)*** which is based upon comorbidities, functional status, and cognition. This scale ranges from 0 (no frailty) to 9 (terminally ill). ***Patient demographics***, including age, race, sex, marital status, years of education, highest occupation, weight, height, and place of residence will be recorded. Hospitalization within 6 months, substance abuse history, and hearing or visual impairment will also be obtained.

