7.1. Primary outcome at 4-months

The primary outcomes for ECID was global cognition at 4-months, as determined by a comprehensive neuropsychological assessment. Global cognition was assessed for using the **Repeatable Battery for the Assessment of Neuropsychological Status (RBANS)**. The RBANS is a comprehensive neuropsychological battery for the evaluation of global cognition

and has been validated in subjects with mild cognitive impairment, moderate to severe traumatic brain injuries, vascular dementias, and Alzheimer’s disease.²³⁻²⁷ In addition to providing a score for global cognition, it also provides individual scores for immediate and delayed memory, attention, visuospatial construction, and language. Scores range from 40 to 160, with higher scores indicating better cognition.

7.2. Secondary Outcomes at 4-months are listed in Table 2.

Study Assessment	Description
Executive function score	Based on the Delis–Kaplan Executive Function System (D-KEFS) Proverbs subscale (conceptual flexibility), the DKEFS Color Word Interference (inhibition), and DKEFS Verbal Fluency Category Switching subscale (monitoring). ²⁸ Scores range from 1 to 18, with higher scores indicating better executive function.
Older American Resources and Services Activities of Daily Living Scale (OARS ADL) ²⁹	Assesses functional status and is based on 7 basic and 7 instrumental activities of daily living. Scores range from 0 (completely dependent) to 28 (completely independent).
EQ-5D-5L ³⁰⁻³²	EQ-5D-5L characterizes quality of life and contains 5-dimensions (“5D”) related to everyday living: mobility, self-care, usual activities, pain/discomfort, and anxiety/depression. EQ-5D-5L index values, validated for the US population, were calculated, and higher scores represented better quality of life. ³³ An index value score of 1.0 indicates perfect quality of life, whereas a score <0.0 indicates quality of life worse than death. The EQ-5D-5L also asks patients to grade their current global health status from 0 (worst health you can imagine) to 100 (best health you can imagine).
Montreal Cognitive Assessment ³⁴	This is a brief test of global cognition based on attention and concentration, executive functions, memory, language, visuoconstructional skills, conceptual thinking, calculations, and orientation. Scores range from 0 to 30, with higher scores indicating better global cognition.
Mortality	Collected by medical record review or informant interview.

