7.3. Index hospital exploratory outcomes

- Delirium duration was defined as the total # of days a patient was delirious or comatose. Delirium was measured daily using the bCAM³⁷ (non-mechanically ventilated) and CAM-ICU³⁸ (mechanically ventilated). We chose the bCAM and CAM-ICU because of their high specificity (>=95%).
- Mean delirium severity throughout hospitalization using the Confusion Assessment Method Severity (CAM-S) scale.³⁹
- Maximum delirium severity throughout hospitalization using the CAM-S
- In-hospital death
- Total number of parenteral (intravenous and intramuscular) doses benzo/antipsychotic medications given during hospitalization adjusting for days in the hospital:
- Hospital length of stay
- ICU length of stay
- Post-discharge disposition in those who survived hospitalization

8. Statistical Methods

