8.1. Descriptive Analysis

To characterize the study sample, demographic, clinical, and lab data will be described overall and by treatment arm. Categorical variables will be described using frequencies and proportions; continuous variables will be described using means and standard deviations as well

as medians and interquartile ranges (IQR) when appropriate. For the proportional odds logistic and logistic regression models, odds ratios (OR) with their 95% confidence intervals (95%CI) will be presented.

8.2. Primary outcome analysis:

Our primary analysis will be an intention-to-treat comparison of 4-month global cognition between those who receive and do not receive the cognitive training and rehabilitation intervention. The association of 4-month global cognition with the cognitive intervention vs usual care will be assessed using proportional odds logistic regression adjusting for a priori defined covariates as listed below in order of priority depending on the degrees of freedom available for each outcome:

Priority	Variable	Description
1	Pre-illness cognition	Quick Dementia Rating System is a 10-item questionnaire ranges from 0 to 30, with higher scores representing greater cognitive impairment. ^{40,41}
2	Pre-illness ADRD	Defined as a QDRS > 6, ⁴⁰⁻⁴² past history of ADRD in the electronic health record, or prescribed a home acetylcholine esterase inhibitor (i.e., donepezil) with ≥ 1 ADL impairment in the pre-illness OARS ADL. ⁴³
3	Age	Age in years at the time of enrollment
4	Pre-illness function	Older American Resources and Services Activities of Daily Living (OARS ADL) scale which assesses 7 basic and 7 instrument ADLs. ²⁹
5	Severity of illness	Acute Physiology Score of the Acute Physiology and Chronic Health Evaluation II (APACHE II) which is based on 12 laboratory, vital sign, and GCS. ⁴⁴
6	Comorbidity burden	Elixhauser comorbidity burden based on 31 comorbid conditions ⁴⁵
7	ADRD*treatment assignment interaction	To determine if cognitive intervention
8	Pre-illness Frailty	Clinical Frailty Scale (CFS) range from 0 (no frailty) to 9 (terminally ill) and is based on patient's comorbidities, and baseline cognition and function. ^{35,46}
9	Years of education	
10	Central nervous system etiology	Determined by 2 expert physician raters. Any disagreement was adjudicated by a third expert physician rater.
11	Race (Black vs non-Black)	
12	Sex	

Table 4. Covariates considered for the multivariable regression models in order of importance.

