The number of covariates incorporated will depend on the number patients with completed 12-month RBANS. We will have one degree of freedom available for every 10 to 15 patients with completed outcome measurements.⁴⁷ If the number of RBANS completed (our primary outcome) is lower than expected, then we will reduce the number of covariates incorporated into the model to minimize overfitting. We will evaluate if the covariates are highly correlated with

each other; if two variables are highly correlated, the lesser priority covariate will be removed. We will not adjust for site (VUMC vs Nashville VA), because the proportion of patients enrolled in the Nashville VA is anticipated to be < 10% of those enrolled. Post-randomization covariates (e.g., interventions provided during hospitalization) will not be adjusted for because they may potentially be affected by the randomized intervention and be on the causal pathway. Unadjusted and adjusted medians with their interquartile ranges (IQR) will be reported for the intervention and usual groups. Unadjusted and adjusted odds ratio (aOR) with their 95% confidence intervals (95%CI) will also be reported.

Multiple imputation for missing covariates based on predictive mean matching will be performed. As with our previous studies, multiple imputation will also be performed for RBANS with partially missing cognitive domains.^{9,48,49} If $\leq 5\%$ of the RBANS is partially missing, then single imputation using a model-based approach will be used to calculate the RBANS global score. If $> 5\%$ of RBANS is partially missing, then multiple imputation will be performed to calculate the RBANS global score. Patients who had completely missing RBANS were removed from the statistical analysis.

8.3. Sensitivity analyses for Primary Outcome:

Several sensitivity analyses will be performed to assess the robustness of our findings:

- 1) We will perform a modified per-protocol analysis will be performed where we will determine if the total duration of cognitive training and total duration of cognitive rehabilitation is associated with our primary outcome. Participants in the usual care group will be assigned cognitive training and cognitive rehabilitation durations of 0.
- 2) We will also see if the intervention is effective in a subset of patients who are only positive for other delirium assessments (bCAM, CAM, 3D-CAM) by repeating the primary analysis on subsets of those positive for each of the listed delirium assessments.

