- 3) To account for the potential differences in survival between the intervention and usual care groups, we will treat death as the worst outcome in those who died before the 4-month follow-up and assign these patients an RBANS score of 39.
- 4) To determine how multiple imputation impacted our findings, we will do a complete case analysis of patient who had missing RBANS.

We will re-run the proportional odd logistic regression models using the same covariates as our primary analysis.

8.4. Heterogeneity of treatment effect analysis for primary outcome:

Because detecting a statistical interaction may require significantly greater statistical power than detecting a main effect, a p-value for the interaction term < 0.20 will be considered as the threshold by which effect modification is potentially present. We will evaluate effect modification of the following variables:

- 1) Age
- 2) Severity of illness as defined by APS of the APACHE II
- 3) Years of education
- 4) Enrollment delirium severity (CAM-S)
- 5) Enrollment psychomotor subtype (hypoactive, hyperactive, mixed, normal)

- 6) Enrollment level of arousal (normal, decreased, increased)
- 7) Enrollment etiology (drug, infection, metabolic/endocrine, organ dysfunction, CNS)
- 8) Time from ED presentation to randomization, which is a surrogate to time to first cognitive intervention
- 9) Hopkins Rehabilitation Engagement Rating Scale (HRERS), which is a measure of patient engagement with the cognitive intervention. Patients in the usual care arm will be assigned a score of 0.

For the heterogeneity of treatment effect analysis, we will re-run the proportional odd logistic regression models using the same covariates as our primary analysis.

8.5. Analyses for Secondary Outcomes: All secondary outcomes analyses will be intention-to-treat using the same approach as our primary outcome.

- 1) Multivariable proportional odds logistic regression will be performed for executive function composite score, MoCA, OARS ADL, and EQ-5D-5L at 4-months using the same covariates.
- 2) For 4-month mortality, multivariable logistic regression will be performed. If there are less than 30 events, only a univariate analysis will be performed.
- 3) For nursing home placement, multivariable logistic regression will be performed. If there are less than 30 events, only a univariate analysis will be performed.

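### The MoCA scheduled in the ED and at 120 hours or discharge has no named role in any analysis, so the 4-month cognitive models carry no tested baseline

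*SAP*

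**What the plan says.** **Schedule.** Protocol Table 4 (section 5.2) has a row for "Montreal Cognitive Assessment (Appendix V"), done with the patient and marked under ED, hospital and 4-month follow-up, without restriction by arm. The footnote fixes the middle time point: "MOCA to be performed at 120 hours or at hospital discharge, whichever comes first". The RBANS and the D-KEFS tests are marked at 4 months only.

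**Outcomes.** SAP Table 2 lists the MoCA as a 4-month secondary outcome ("This is a brief test of global cognition based on attention and concentration, executive functions, memory, language" and other domains). SAP 8.5 item 1 models "executive function composite score, MoCA, OARS ADL, and EQ-5D-5L at 4-months using the same covariates". The SAP's index-hospital exploratory outcomes include delirium duration, "Mean delirium severity throughout hospitalization using the Confusion Assessment Method Severity (CAM-S) scale" and its maximum, in-hospital death, parenteral drug doses, lengths of stay and disposition. The MoCA is not among them.

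**Covariates.** SAP Table 4 ranks 12 rows. The first is the QDRS ("Quick Dementia Rating System is a 10-item questionnaire ranges from 0 to 30") and the second is pre-illness ADRD, for which a QDRS cut-off is one of the qualifying criteria. Protocol 5.2.c takes the QDRS and eCOG "scales from a qualified informant (caregiver, offspring, spouse, sibling, or having known the patient >5 years"). Protocol Table C8.1.a adds propositional density from old writing samples, which the SAP list does not carry. SAP 8.2 says that post-randomisation covariates "will not be adjusted for because they may potentially be affected by the randomized intervention and be on the causal pathway".

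**The concern.** Two MoCA assessments are scheduled in an acutely ill population, and no covariate list, effect-modifier list, index-hospital outcome or latent-class input names either one. Neither document gives a reason.

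This sits awkwardly with the plan's own logic. Protocol 9.1 justifies covariate adjustment by the power it can add, and a cognitive score from the patient at enrolment is an obvious candidate for a cognitive outcome. The OARS ADL recorded at enrolment is covariate 4, so the 4-month OARS ADL is adjusted for its own earlier value. The 4-month MoCA is not. Protocol 5.4 also sets out to study the effect of training on index-hospital outcomes, yet the one global cognition test between enrolment and 4 months is left off that list.

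At stake are some precision in the 4-month cognitive comparisons, and a direct look at global cognition at the end of the inpatient phase.

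**Working it through.** **1. Where each MoCA value is used**

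| Place | ED MoCA | 120-hour/discharge MoCA |
|---|---|---|
| SAP Table 4 covariates (12 rows) | not named | not named; barred as post-randomisation |
| SAP 8.4 effect modifiers | not named | not named |
| SAP index-hospital exploratory outcomes | does not apply | not named |
| SAP 8.5 model for 4-month MoCA | not named | not named |
| Protocol Table C8.1.a and section 9.1 | not named | not named |
| Protocol 9.3 latent-class inputs | not named | not named |

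**2. The plan's sample size (SAP 8.7)**

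Inputs: SD 12.4, difference 6.0, two-sided alpha 0.05, power 80%, allocation 1:2. With m in the intervention arm and 2m in usual care, the normal approximation gives

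m = 1.5 × (1.960 + 0.842)² × 12.4² / 6.0² ≈ 50.3,

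that is 51 + 101 = 152. The noncentral t version gives 51 + 102 = 153 with power 0.8005, matching the SAP. For attrition, 51 / (0.70 × 0.78) = 93.4, rounded up to 94, and 94 × 3 = 282, also matching. The sample size is sound.

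**3. What an enrolment MoCA could add**

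Let r be the partial correlation of the enrolment MoCA with the 4-month score, given the other covariates. The documents give no value, so r is assumed. In a linear model the residual variance falls by r², and the equivalent number of extra completers is 153/(1 − r²) − 153. Power at 51 + 102 uses the normal approximation with residual SD 12.4 × √(1 − r²), taking 12.4 as the residual SD before the MoCA is added.

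| Assumed r | Variance reduction | Extra completers | Power for 6.0 points |
|---|---|---|---|
| 0 | 0% | 0 | 80.6% |
| 0.1 | 1% | 1.5 (about 2) | 80.9% |
| 0.2 | 4% | 6 | 82.1% |
| 0.3 | 9% | 15 | 84.1% |
| 0.5 | 25% | 51 | 90.3% |

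The SAP model is proportional odds, where another prognostic covariate also changes the conditional odds ratio being estimated. The table is an analogy, not a forecast.

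**4. Degrees of freedom**

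SAP 8.2 allows 1 df per 10 to 15 completers: 153/15 = 10.2 and 153/10 = 15.3. Treatment plus 12 rows at 1 df each is 13, or 14 with the MoCA. At 1 per 10 that fits. At 1 per 15, treatment plus the first nine rows uses all 10, and row nine is years of education. A MoCA ranked directly after ADRD would push education out.

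**The case against.** The plan adjusts for cognition before the illness, which is a defensible choice. Every patient is delirious at enrolment, so an ED MoCA partly measures acute delirium, and its partial correlation with a 4-month score may be small. At r = 0.1 the gain is negligible. This stands as a limit on size. It does not explain the silence, since a value measured during delirium is still a legitimate covariate if taken before randomisation.

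That condition is not documented. The protocol places only the delirium screen before consent, with randomisation after consent, and Protocol Table 4 gives the MoCA just an ED column. A reader might take it as a pre-randomisation measure, but the documents never say so. If it came later, the SAP's own rule would bar it.

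Two further inferences go too far. A reader might conclude that the early MoCA is used nowhere. SAP 8.1 describes clinical data by arm and could include it, and SAP 8.2 does not list its imputation predictors, so the supportable statement is that no analysis names it. A reader might also conclude that nothing examines the inpatient phase. Delirium duration and CAM-S severity do, and SAP 8.3 item 1 enters training and rehabilitation durations separately, though that dose comparison is not randomised. What is missing is a global cognition test.

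Timing is a fair objection too. The SAP is version 2.4, dated November 2024, and describes enrolment in the past tense, so changing the primary model's covariates is more than a wording edit.

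**Conclusion.** The point holds as a minor one about precision and completeness. Two scheduled MoCA values have no named analysis. As a result the 4-month MoCA is modelled without its enrolment value, the RBANS and executive-function models rest on informant QDRS and the ADRD flag alone for baseline cognition, and the index-hospital outcomes contain no global cognition test.

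A reader might infer a biased treatment comparison or a faulty sample size. Neither follows: omitting a baseline covariate does not bias a randomised comparison, and 153 and 282 both reproduce.

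The gain from using the enrolment value ranges from about 2 to 51 completer equivalents over an assumed partial r of 0.1 to 0.5. It rests on that unknown correlation, on a linear-model analogy, and on the ED MoCA preceding randomisation.

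**What to change.** - **Confirm timing.** State in the SAP whether the ED MoCA is taken before randomisation. The next two items apply only if it is.
- **4-month MoCA model.** Add the ED MoCA as a covariate with an explicit rank.
- **RBANS and executive-function models.** Do the same if the SAP can still be changed before outcomes by arm are seen. Otherwise report the MoCA-adjusted fits as sensitivity analyses labelled as such before they are run.
- **Missing values.** Use the covariate imputation already planned in SAP 8.2.
- **120-hour/discharge MoCA.** List it as an exploratory index-hospital outcome, compared unadjusted as SAP 8.6 prescribes. If a comparison adjusted for the ED MoCA is also wanted, state it as an exception to 8.6.
- **If either value is left out,** say so and give the reason.

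The data are already scheduled. The cost is 1 df, some imputed values for patients who could not be tested and, at 1 df per 15 completers with the MoCA ranked directly after ADRD, the loss of years of education from the model. Education is also an effect modifier in SAP 8.4, so its main effect would need to be kept in that analysis.

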5.4. Outcome Variables for Aim #1 (randomized control trial)

Four months (3 to 7 months) after randomization, subjects will return to the local site for outcome ascertainment. For those who are unable to travel, a member of the neuropsychological team will travel to the patient's home. The primary and secondary outcome variables to be collected at 4-months (range 3 to 7 months) are listed in **Table 4**. We will also investigate the effect of cognitive training on **index hospital outcomes** as part of our secondary analyses. We will collect delirium duration using the modified bCAM, and hospital length of stay, ICU length of stay, and post-discharge disposition (e.g., skilled nursing facility) to be collected via medical record review. Based upon the neuropsychological raters' observations, they will also determine the Clinical Frailty Scale (Appendix N). They will also collect the **Mini-Nutritional Assessment (Appendix M)** for covariate adjustment.

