Permanent nursing home placement	Collected by patient or informant interview.

Table 2. Secondary outcomes for ECID.

7.3. Exploratory Outcomes at 4-months are listed in Table 3.

Study Assessment	Description
Individual RBANS subscale domains	Scores for each RBANS individual cognitive will be reported - Immediate and delayed memory, attention, language, visuospatial construction.
Individual D-KEF domains	Individual scores for each DKEF Subscale that make up the Executive Function Composite Score will be reported - Proverbs (conceptual scale flexibility), Color Word Interference (inhibition), and Verbal Fluency Category switching (monitoring).
Clinical Frailty Score ³⁵	Characterizes frailty and is based on comorbidities, functional status, and cognition. This scale ranges from 0 (no frailty) to 9 (terminally ill).
Life Space Assessment ³⁶	Characterizes mobility and physical activity by asking 9 questions characterizing the patient’s movement within his/her environment over the past 3 days.
Rehospitalization	Collected by medical record review or informant interview.

Table 3. Exploratory outcomes at 4 months.

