We will adjust for the same covariates as the primary analysis. However, the number of covariates incorporated will depend on the number patients and events for the proportional odds logistic regression and logistic regression models, respectively. For our proportional odds logistic regression model, we will have one degree of freedom available for every 10 to 15 patients with completed outcome measurements.⁴⁷ For our multivariable logistic regression models, we will have one degree of freedom available for every 10 to 15 outcomes for our multiple logistic regression models.⁴⁷ We will incorporate the covariates in order of importance. Proportions and medians with their IQR will be reported for the intervention and usual groups for categorical and continuous outcomes, respectively. Unadjusted and adjusted odds ratio (aOR) with their 95% confidence intervals (95%CI) will also be reported.

8.6. Analysis for Exploratory Outcomes (4-month and index hospitalization): All exploratory outcomes analyses will be intention-to-treat. For these outcomes, unadjusted comparisons using the Wilcoxon Rank-sum tests or chi-squared test will be performed for continuous and categorical variables, respectively. Unadjusted odds ratios will be reported. A p-value < 0.05 will be considered statistically significant.

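### SAP 8.6 compares 4-month Clinical Frailty Scale and Life Space without adjustment, although Protocol Table 4 schedules both at enrolment: a small, cheaply recovered loss of precision on exploratory outcomes

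*SAP*

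**What the plan says.** SAP Table 3 lists five exploratory outcomes at 4 months: RBANS domains, D-KEFS subscales, CFS, Life Space and rehospitalisation. Section 8.6 covers them all: "unadjusted comparisons using the Wilcoxon Rank-sum tests or chi-squared test will be performed for continuous and categorical variables, respectively". It reports unadjusted odds ratios and calls p < 0.05 significant.

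Protocol Table 4 marks "Clinical Frailty Scale (Appendix N") and "Life Space Assessment (Appendix F") in both the ED and the 4-month columns. "Repeatable Battery for the Assessment of Neuropsychological Status (RBANS, Appendix O") and the D-KEFS tests are marked at 4 months only. CFS and Life Space are therefore the only exploratory 4-month outcomes with an enrolment value on the same scale.

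At enrolment, Protocol 5.2.d uses CFS to rate pre-illness frailty, "based upon comorbidities, functional status, and cognition". At 4 months, Protocol 5.4 says of the neuropsychological raters that "they will also determine the Clinical Frailty Scale (Appendix N"). SAP Table 3 describes Life Space as covering "movement within his/her environment over the past 3 days".

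SAP Table 4 places pre-illness frailty at priority 8 of 12: "Clinical Frailty Scale (CFS) range from 0 (no frailty) to 9 (terminally ill"). SAP 8.2 and 8.5 use that list for the primary and secondary outcomes, subject to the degrees-of-freedom limit and to removal of the lower-priority member of a highly correlated pair.

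**The concern.** The plan treats comparable measures differently. OARS ADL, also collected at enrolment and at 4 months, gets a model whose covariate list includes its own pre-illness value (priority 4). Pre-illness CFS may be used to adjust 4-month RBANS, yet it is not used for 4-month CFS. Protocol 9.1 itself argues that adjusting for strong predictors can raise power, and the SAP gives no reason for stopping short here.

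At stake is the precision of two exploratory comparisons. An unadjusted test leaves in the outcome the variation that the enrolment value would explain, and it does not correct for a chance difference between arms at enrolment.

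**Working it through.** **The plan's own figure.** SAP 8.7 gives SD 12.4, difference 6.0, two-sided alpha 0.05, 80% power and 1:2 allocation. The normal formula gives 101 + 50.5 = 151.5 patients against the stated 153. At 51 versus 102 the noncentral t power is 80.05%. Enrolment: 153 / (0.70 × 0.78) = 280.2, so 281 against the stated 282. Both reproduce within two patients. The documents state no power for CFS or Life Space, so 51 versus 102 is carried over as an assumption.

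**What adjustment buys.** In a linear approximation, adjusting for an enrolment value with correlation r multiplies the outcome variance by 1 − r². The standard error of a difference, in SD units, is √(1/51 + 1/102) = 0.171. The effect detectable with 80% power is (1.960 + 0.842) × 0.171 × √(1 − r²): 0.480 SD at r = 0, 0.458 at r = 0.3 and 0.416 at r = 0.5.

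**Power for a 0.5 SD shift (assumed), two-sided 0.05.** For CFS, outcome and baseline were cut from bivariate normals into 10 levels (the SAP's 0 to 9 range), with 3,000 runs per cell. The Wilcoxon test was compared with the likelihood-ratio test in a proportional odds model containing treatment and baseline. The skewed margins, for levels 0 to 9, were assumed as .01 .01 .02 .06 .12 .18 .28 .24 .07 .01. The SAP gives no score range for Life Space, so its column is a linear approximation (noncentral t, 150 df).

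| r (assumed) | CFS, even margins: Wilcoxon → adjusted | CFS, skewed margins: Wilcoxon → adjusted | Life Space: adjusted (unadjusted t 82.6%) |
|---|---|---|---|
| 0 | 80.4 → 80.7% | 79.5 → 79.6% | not applicable |
| 0.1 | 80.0 → 80.8% | 80.1 → 80.7% | 82.9% |
| 0.3 | 79.1 → 82.5% | 78.6 → 82.8% | 85.9% |
| 0.5 | 80.9 → 89.6% | 79.0 → 88.5% | 91.7% |

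The Monte Carlo standard error is at most 0.8 point. With no treatment effect, the Wilcoxon test rejected in 4.2 to 5.7% of runs and the proportional odds test in 4.9 to 6.1%, so part of the smallest gains comes from a slightly liberal test. The Life Space reference is a t-test, not the planned Wilcoxon. Under normality the Wilcoxon would have about Φ(0.5 × √(3/π) / 0.1715 − 1.96) = 81.3%. That 1.3-point gap is a difference between tests, not a gain from adjustment.

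**Chance imbalance.** A baseline gap of at least 0.25 SD has probability 2 × [1 − Φ(0.25 / 0.1715)] = 0.145. It carries into the outcome as 0.25 × r, which is 0.025 to 0.125 SD for r = 0.1 to 0.5.

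**Cost if the baseline is useless.** One added covariate inflates the variance by (153 − 3) / (153 − 4) = 150/149 = 1.0067, about 0.7%. Break-even is where (1 − r²) × 150/149 = 1, so r = √(1/150) = 0.082.

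**Degrees of freedom.** The SAP's rule allows 153/15 = 10.2 to 153/10 = 15.3. A model with treatment and one baseline uses 2. In the primary model, treatment plus priorities 1 to 8 uses 9, so pre-illness CFS fits there at the planned size unless the collinearity rule removes it.

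**The case against.** The strongest reply is that the SAP is deliberately tiered: adjusted models for primary and secondary outcomes, simple tests for exploratory ones. That is a defensible design, and neither CFS nor Life Space is powered or decides the trial. This stands, and it limits the weight of the point.

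Several further objections also stand:

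- The size rests on an assumed r. At r = 0.1 the CFS gain (0.6 to 0.8 point) is within simulation error.
- The two CFS ratings differ in reference period, and the 4-month one is made by the neuropsychological raters; both features may lower r.
- Pre-illness CFS is only a candidate covariate. It draws on comorbidity, function and cognition, which priorities 1, 4 and 6 already cover, so the collinearity rule could remove it.
- The Life Space baseline is thinly documented. Its enrolment collection rests on one table entry, and Protocol 5.2.d does not mention it. Protocol 9.1 uses mean Life Space scores as a measure of activity during rehabilitation. No text says the ED value precedes randomisation, and a 3-day window in the ED may capture the acute illness.
- An adjusted result beside an unadjusted one gives two chances at p < 0.05 unless one is named as governing.

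A reader might infer that the unadjusted tests are biased. The documents do not support that: arms are randomised and a chance gap is part of the test's error rate. Analysing only patients assessed at 4 months, about 0.70 × 0.78 = 55% of those enrolled at the planned attrition, is a separate problem, which baseline adjustment does not settle.

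A reader might also extend the point to the 4-month MoCA model in 8.5. No gain is shown there. At 15 patients per df, enrolment MoCA would displace years of education. With a partial correlation of 0.2 for MoCA, against 0.1, 0.2 or 0.3 for education, the ratio (1 − r²) for education over (1 − r²) for MoCA is 0.99/0.96, 0.96/0.96 or 0.91/0.96: +3%, 0 or −5%.

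**Conclusion.** The point holds as a low-severity suggestion. The plan collects an enrolment value for CFS and schedules one for Life Space, but uses neither when analysing the same measure at 4 months. The result is lost precision on two exploratory outcomes. It is not an invalid test, and it does not affect the primary conclusion.

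The gain is under 1 power point at r = 0.1, about 3 to 4 at r = 0.3 and about 9 to 10 at r = 0.5. These figures assume 51 versus 102 patients with outcomes, a 0.5 SD shift and the stated score distributions; r itself is unknown. The case is firmer for CFS than for Life Space.

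**What to change.** Settle this before outcomes are examined by arm.

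- **CFS.** In SAP 8.6, analyse 4-month CFS with a proportional odds model containing treatment and pre-illness CFS. Name it as the one analysis to which the p < 0.05 rule applies, and report the unadjusted comparison as supportive only.
- **Life Space.** Do the same only where the enrolment value was recorded before randomisation, and note that the 3-day window may reflect the acute illness and reduce the gain.
- **Everything else.** Leave the remaining exploratory outcomes and the MoCA model as planned.

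The cost is SAP wording and a little more analysis, with no new data collection. The adjusted odds ratio is conditional and will not equal the unadjusted one, so both need labels. The model adds a proportional-odds assumption, and missing enrolment values need the covariate imputation already planned in 8.2. If r is 0, about 0.7% of efficiency is lost.
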